### **5.3. Randomization**

A participant’s AHI estimate from the first clinic visit determines whether she is randomized, assigned to the control group for observation only, or withdrawn from the study.

Participants with an AHI estimate below 5 are assigned to the control group. They are not randomized.

Participants with an AHI estimate of 50 or higher are referred to a sleep specialist and withdrawn from the study. They are not randomized.

Participants with an AHI estimate 5-49 who agree to randomization receive an autotitrating- or sham-CPAP machine. Autotitrating units coordinate air-flow delivery with effort to provide the lowest pressure necessary to maintain upper airway patency. Sham units have a hidden leak. This is a double-blind study, so neither participants nor clinical personnel are supposed to know which CPAP machines are active versus sham. The DCC stores randomization assignments separately; they are not part of the electronic Data Management System.

**Table 4: AHI Estimates, Study Assignment, and Instructions for SBNC**

AHI Estimate	Assignment	Instructions for SBNC
<5	Control	Tell participant that she does not have sleep apnea so she will not be in the treatment part of the study. Do not randomize.
5-49	CPAP ("Case")	Tell participant that she is eligible for the treatment part of the study and ask if she agrees to be randomized. If she agrees, proceed with randomization (see Instructions, below). If she does not agree: 1) do not randomize; 2) notify Study Coordinator immediately.
≥50	Withdrawn	Tell participant that she has a degree of sleep apnea that requires attention and let her know that the Study Coordinator will follow up to provide a referral to a sleep specialist. Notify Study Coordinator immediately. Do not randomize.

**Instructions: Randomization**

- 1) Refer to the Randomization Log, stored in the supply room with the CPAP machines at the SBNC.

**SOAP**

RANDOMIZATION LOG

This log should remain with unassigned CPAP units

CPAP UNIT NUMBER	TAKEN BY	DATE TAKEN	ASSIGNED TO [SOAP ID]
C001	_____	__/__/__	_____ - _____
C002	_____	__/__/__	_____ - _____
C003	_____	__/__/__	_____ - _____

- 2) Refer to the Randomization Log, stored in the supply room with the CPAP machines at the SBNC.
- 3) Select the next consecutive CPAP unit number from the list. It is important not to skip any rows.
- 4) Select the CPAP carrying case that matches the number from the log. Open the case to make sure the unit number on the machine, elbow bag and elbow all match. If they do not match, or if any component is missing, make a note on the Randomization log, select the next consecutive CPAP unit number, and notify the Study Coordinator immediately.
- 5) Complete the Randomization log with your initials, the date, and the participant's SOAP1 ID. Record the same information, plus the CPAP unit number, mask type and size, on the SSA.
- 6) Pick up the mask that the participant was fitted for the night before and attach the elbow located inside the CPAP case.
- 7) Train the participant on proper CPAP usage, cleaning, etc.
- 8) Give the CPAP case to the participant.

**5.4. CPAP Equipment**

The PI is responsible for obtaining active and sham CPAP machines and elbows along with cases and modems. The DCC assembles units in batches, at the request of the PI, attaching modems and labeling components. The coordinator brings the units to the SBNC for distribution to eligible participants at Clinic Visit 1.

## Sleep-Disordered Breathing, Obesity and Pregnancy, Protocol 1 (SOAP1)

---

Each CPAP unit has a built-in hard drive that stores up to six months of data, a removable memory card that stores up to one year of data, and a modem configured to transmit data electronically. Data are transmitted to a secure, password-protected website ([encoreanywhere.com](http://encoreanywhere.com)) and are reviewed regularly by the PI to assess compliance and determine if the participant is eligible for incentive payments (see “Participant Compensation,” below). Data are accurate in real time only if modems are working properly. Otherwise, there may be a lag until data from the memory cards are transmitted.

### **Instructions: Labeling CPAP Machines**

- 1) The PI requests machines from the manufacturer, along with active and sham elbows, and notifies the DCC when they arrive.
- 2) To keep the clinical staff blinded, the DCC assembles kits – including the CPAP machine, a modem, and elbow – and labels all of the parts with the circuit number. Kits are stored in canvas bags.
- 3) The Clinical Team delivers the labeled kits to WPIC.

### **5.5. Home Visit and Weekly Calls/Texts**

CPAP participants are scheduled for a follow-up Home Visit (HV) by study personnel to try to address potential barriers to CPAP utilization. There is no defined window but, ideally, the visit occurs within two weeks of randomization. Additional visits may be scheduled, if needed. In addition to the home visit, the coordinator attempts to contact participants weekly by phone, text and/or email, depending on preferences recorded on the Contact Information (CI) form, to remind them to continue to use their CPAP machine.

### **5.6. Delivery/Post-Delivery**

To ensure that Magee is prepared for SOAP deliveries, the Study Coordinator uses UPMC's Augr website to report medical record numbers (MRNs) of patients who are participating in the study, adding new enrollees and removing those who have already delivered or been withdrawn. In addition, she emails the same information directly to the Magee Obstetric Sterile Processing Unit (OSPU), as a backup measure. At delivery, cord blood is collected, placental biopsies are taken, and the placenta is sent to the Pathology Department, as documented by the OSPU on the Delivery Specimen (DS) form. If the OSPU is not staffed at the time of delivery, or the participant delivers at a non-study hospital, it is possible that specimen will not be collected.

The Pathology Department prepares and stores slides of the placenta for future analysis by [name], a study co-PI. Cord blood and plasma are stored by the OSPU, for possible future analysis.

For randomized participants, the coordinator documents IDSMB Outcomes (D0), administers a CPAP Survey (CS), consults the DCC to be Unblinded (UB) about the status of the CPAP unit (active versus sham), unblinds the participant, and, if sham, exchanges her unit with an active one, ideally before she leaves the hospital. In addition, a referral to a sleep specialist is provided, as appropriate, so that follow-up treatment can be arranged.

### Process: Unblinding

1. The Study Coordinator notifies the DCC when she is ready to be unblinded. This should not happen until the DSMB Outcomes (DO) form and CPAP Survey (CS) have been completed.
2. The DCC provides the circuit number of the machine that was issued and the unit type (active or sham).
3. After confirming that the circuit number matches, the Study Coordinator unblinds the participant and collects the modem.
4. If the unit is sham, the Study Coordinator exchanges the unit with an active one, recording the serial number of the active unit replacement, and replaces the sham elbow with an active elbow.

Within four weeks of delivery, a Chart Abstraction (CA) is completed to document lab results and other data related to admission and delivery, labor, maternal complications during pregnancy, postpartum complications, pregnancy outcomes, neonatal care, infant status, etc. CAs are completed by a trained chart abstractor. Prior to entry into REDCap, the following CAs must be reviewed by [name]:

- All CPAP participants
- For non CPAP participants:
  - If delivery occurred before 34 weeks
  - If Yes to any part of section G
  - If Yes to any part of section H
  - If Yes to M1, M2 or M4
  - If Yes to any part of section P

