## 2. Study Overview

Sleep-Disordered Breathing, Obesity and Pregnancy, Protocol 1 (SOAP1) is a prospective observational study of the interplay between sleep-disordered breathing (SDB), obesity and cardiovascular risk factors in pregnancy. Our central hypothesis is that SDB is an effect modifier that increases maternal cardiovascular risk and placental hypoxic injury in obese pregnant women, and that CPAP treatment during pregnancy results in an improved cardiovascular risk and placental profile. To test this hypothesis, our cohort includes obese women with and without SDB. Refer to the table below and sections 1.1-1.4 for a discussion of the protocol. Modifications to this protocol are made only with approval from the IRB and IDSMB.

After a screening process, eligible participants are scheduled for two clinic visits, one during the second trimester (14-20 6/7 weeks) and the other during third trimester (28-31 6/7 weeks). Each visit begins with a questionnaire followed by an overnight polysomnogram (PSG). The following morning, clinical measurements are taken, maternal bloods are collected, and a uterine artery Doppler is performed. Participants with severe apnea at the first clinic visit (i.e., AHI estimate  $\geq 50$ ) are withdrawn from the study. Those without SDB (i.e., AHI estimate  $< 5$ ) are assigned to a control group for observation only. Participants with SDB (i.e., AHI estimate 5-49) are randomly assigned to receive an autotitrating CPAP machine or a sham unit. Autotitrating units coordinate air-flow delivery with effort, providing the lowest pressure necessary to maintain upper airway patency. Sham units, meanwhile, have been modified to deliver air without pressure. Assignment is "double blinded," i.e., neither participants nor members of the clinical research team know which units are autotitrating versus sham. All CPAP units include a modem that transmits data back to the study team. After delivery, SDB participants are unblinded, modems are removed, sham units are replaced with active ones, and referrals to sleep specialists are provided so that appropriate follow-up treatment can be arranged. Data collection points and related forms are discussed in Chapter 5.

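### SOAP1 does not require chart abstraction before the coordinator is unblinded, or by someone unaware of the unit type, so maternal diagnoses are likely to be abstracted with knowledge of arm

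*Protocol*

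**What the plan says.** The SOAP1 manual describes a double-blind comparison. Its Study Overview states that "neither participants nor members of the clinical research team know which units are autotitrating versus sham", and section 5.3 repeats the rule for staff: "so neither participants nor clinical personnel are supposed to know which CPAP machines are active versus sham". Section 6.2 lists unmasking of participants or staff as a protocol violation.

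After delivery (section 5.6), the coordinator completes the DO form, administers the CPAP Survey, is told the unit type by the data coordinating center and tells the participant. If the unit is sham, she "exchanges her unit with an active one, ideally before she leaves the hospital". The unblinding instructions set one condition on timing: "This should not happen until the DSMB Outcomes (DO) form and CPAP Survey (CS) have been completed".

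The same instructions then turn to the chart: "Within four weeks of delivery, a Chart Abstraction (CA) is completed to document lab results and other data related to admission and delivery". Its content includes "maternal complications during pregnancy, postpartum complications, pregnancy outcomes, neonatal care, infant status". They assign the work to a trained chart abstractor and require one named person to review the abstraction of every CPAP participant before data entry. Table 2 instead assigns the Chart Abstraction to the coordinator, in consultation with the principal investigator. It also gives her the Unblinding form.

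The SAP (A. Outcome Ascertainment) discusses abstraction by unblinded staff only as a result of moving to the open design. It argues there that the diagnoses are well defined and backed by laboratory and blood pressure records.

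**The concern.** Masking protects an outcome only until the person recording it learns the arm. SOAP1 secures this for the DO form by placing it before disclosure, but sets no such order for the Chart Abstraction. The abstraction is where maternal diagnoses such as preeclampsia and gestational diabetes are recorded.

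At stake is whether those clinical outcomes can be reported as masked. Because the SAP treats unblinded abstraction as something the open design would introduce, a reader of the results could assume that SOAP1 abstraction was masked. The manual does not ensure that. An abstractor who knows the arm may search a chart harder, or resolve an unclear entry differently, in one group.

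**Working it through.** No figure in the plan depends on this point, so the check sets the texts side by side.

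1. **Who learns the unit type.** The coordinator does (section 5.6; Table 2, Unblinding row).
2. **When.** After the DO form and CPAP Survey, and ideally before hospital discharge (section 5.6).
3. **When the chart is abstracted.** Within four weeks of delivery. No order relative to unblinding is given.
4. **Whether a complete abstraction could come first.** Section 8.1 says the abstraction includes admission and discharge dates, and section 5.6 adds postpartum complications and infant status. Where unblinding does occur before discharge, the abstraction can hardly be complete by then. The plan's own preferred timing therefore makes abstraction after unblinding the usual order.
5. **Who abstracts.** Table 2 says the coordinator; section 5.6 says a trained abstractor. Section 4.2 gives abstraction training to the clinical team, so these may be the same person. Neither place states whether the abstractor or the reviewer knows the unit type.
6. **Whether the DO form already covers these diagnoses.** Section 6.1 says it records adverse pregnancy outcomes for CPAP participants. The examples there, and the four safety outcomes in section 3.4 and in the SAP, are pregnancy loss and fetal or neonatal events. Preeclampsia and gestational diabetes are not among them. The form itself is not in the documents, so this rests on the outcomes listed.
7. **What lies outside the problem.** The SAP's three domain primary measures are uterine artery Doppler pulsatility index, the sFLT/PlGF ratio and HOMA-IR. They come from ultrasound and blood at the clinic visits. Aim 3 uses the placental profile. None is taken from chart abstraction.
8. **How much can still be changed prospectively.** The SAP reports 43 women randomized by 14 February 2017, of 45 planned for the sham comparison. The current SOAP1 manual is dated 22 September 2017, which is 220 days, or 220/7 = 31.4 weeks, later. Randomization takes place at Visit 1, at 14 weeks or more, so those 43 women would have reached at least 14 + 31.4 = 45.4 weeks. All of those pregnancies had therefore ended, and correcting completed records and their reporting matters most.

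**The case against.** The strongest reply is that nothing in the manual says abstraction was unblinded. A reader might infer that the coordinator is told the arm and afterwards abstracts every chart. The text does not say so: only a deadline is set, an abstraction done before unblinding would comply, and section 5.6 does not name the coordinator. This stands. Knowledge of arm is permitted and likely, but it is not prescribed.

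It also stands that safeguards exist. The SAP's reasoning about well-defined, documented diagnoses concerns the outcomes themselves and applies equally to SOAP1. Every CPAP participant's abstraction has a second review. Chart entries made during pregnancy predate the planned unblinding, so what remains open is mainly how the record is read, plus entries made after disclosure.

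Two further readings go too far. One is that SOAP1 is the only phase that could supply masked clinical outcomes; an abstractor who has not been told the arm can also work in an open-label phase. The other is that all 45 planned women are affected. That would require every abstraction to have followed unblinding, and it ignores withdrawals, after which section 6.3 stops data collection.

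Finally, the SAP calls the CPAP trial a pilot that is not meant to settle effectiveness. That lowers the stakes, but it does not make the outcomes masked.

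**Conclusion.** The concern holds as a minor gap. SOAP1 neither places chart abstraction before unblinding nor reserves it for someone unaware of the unit type, and it gives two accounts of who abstracts. With unblinding ideally before discharge, maternal diagnoses in the double-blind phase are likely to be abstracted with knowledge of arm.

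The direction and size of any bias are unknown, and nothing in the documents allows an estimate. Documentation and second review probably keep it small. The conclusions on the three domain primary measures and the placental outcome are not touched by this point.

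The verdict assumes that the preferred timing of unblinding was usually met, that the trained abstractor is the coordinator or someone else who knew the unit type, and that the DO form holds no maternal diagnoses beyond the outcomes listed. Form dates and staff initials could overturn the first two assumptions, and the form itself the third.

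**What to change.** 1. Reconcile Table 2 and section 5.6 of the SOAP1 manual on who abstracts, and state whether the abstractor and the reviewer may know the unit type.
2. For any randomized woman not yet unblinded, record the maternal diagnoses known by delivery on the DO form, or complete those sections of the abstraction, before the data coordinating center discloses the unit type. The unit exchange should not be delayed for this. Where existing staff allow, have the later abstraction or its required review done by someone who has not received the unit type.
3. For completed records, compare the date of abstraction with the date of unblinding, note who abstracted, and report how many abstractions followed unblinding. Do not describe the outcomes from those records as masked. Abstractions are made on paper before entry (section 7), so use the form date and initials, since the REDCap entry date may be later. The revision log shows that abstraction procedures changed in September 2016 and that the DO-form condition entered the manual in July 2017. Read the sequence from each record and do not assume that the current rules applied throughout.

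The cost is a few extra DO-form items and a comparison of dates already held. Diagnoses that arise after unblinding, chiefly postpartum ones, would still not be covered. A separate masked abstractor cannot be taken for granted: section 3.2 lists one coordinator and one research assistant, and nothing shows that the assistant is trained to abstract.

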### 5.7. Participant Compensation

All participants are eligible to receive up to \$550 for completing the following procedures:

- PSG (clinic visits 1 and 2):  $\$150 \times 2 = \$300$
- Maternal bloods (clinic visits 1 and 2):  $\$50 \times 2 = \$100$
- Uterine artery Doppler (clinic visits 1 and 2):  $\$75 \times 2 = \$150$

In addition, CPAP participants are eligible for the following payments:

- CPAP compliance incentive:  $\$10/\text{week}^2$
- CPAP survey (delivery/post-delivery): \$25
- CPAP return (delivery/post-delivery): \$40

The coordinator uses the web-based WePay™ card payment system to disburse payments to participants. In addition, free parking is provided at Magee and WPIC, for sleep studies.

#### Instructions: WePay

1. Log on at <https://wepay.upmc.com/WP>
2. Select "Make a Payment"
3. Pick a known participant or search for or create a new participant
4. Activate a new card for new participants or select the payment card for return participants
5. Enter compensation, reimbursement and participant ID
6. Select "Continue" to print a receipt for the participant

---

 Compliance is defined as using the CPAP a minimum of 4 hours per day for at least 5 out of 7 days.

## 6. Events

### 6.1. Adverse and Serious Adverse Events, including Adverse Pregnancy Outcomes

Over the course of any study, there is always a risk of an adverse event, defined as the unintended worsening of a participant's signs or symptoms. AEs are characterized in terms of study-relatedness, expectedness, and seriousness.

The SOAP1 informed consent form includes a list of AEs considered both "study related" and "expected":

- Minor discomfort associated with wearing the belt, nasal cannula and/or finger pulse oximeter during the ApneaLink Home Sleep Monitoring
- Mild bleeding, bruising, and/or soreness (infrequent; occurs in 1%-10% of people) during blood draws. Other risks include fainting and/or infection (rare; occurs in less than 1%)
- Rash or chafing at the site of the monitors, probes and/or electrodes during the PSGs
- Brief and/or minor discomfort associated with CPAP use (e.g., minor skin discomfort from the mask, nasal stuffiness, runny nose, nosebleed, eye discomfort)
- Rash or chafing at the site of the uterine artery Doppler abdominal US probe

For this study, adverse pregnancy outcomes (APOs) are also considered "expected," even though they are not on the informed consent form, because they can, theoretically, happen in any pregnancy. Examples include miscarriage, preterm birth, severe growth restriction, intrauterine fetal demise, and neonatal death before discharge. To determine whether APOs are study-related requires unmasking so this is handled by the IDSMB (see below).

An AE is considered serious if:

[figure not shown]
- it is life threatening;
- it results in death, hospitalization (initial or prolonged), or disability or permanent damage; or
- an intervention is required to prevent permanent impairment/damage.

Serious adverse events (SAEs) that are unexpected and related, or possibly related, to the study must be reported by the PI to the University of Pittsburgh HRPO as soon as possible but no more 24 hours after discovery. SAE reporting is done online through the HRPO's OSIRIS electronic submission system.

Meanwhile, every non-APO SAE, irrespective of relatedness and expectedness, must be reported by the PI to the chair of the IDSMB and NHLBI staff, within 48 hours of discovery.

Miscarriages are documented on a Withdrawal (WD) form; all other APOs are documented during Chart Abstraction (CA) following delivery. For CPAP participants, APOs are also documented on the IDSMB Outcomes (DO) form. All other AEs are documented on Adverse Event (AE) forms. AE and APO data are pulled for weekly internal "Events" reports and are also included in bi-annual reports to the IDSMB. IDSMB reports are unmasked so that members can determine study-relatedness (e.g., evidence of a deleterious effect of sham-CPAP treatment on the fetus) and consider whether the study needs to be modified or even terminated. Documentation and reporting requirements are summarized in the Diagram 1, below.

**Diagram 1: Documenting and Reporting AEs and SAEs, including APOs**

## 6.2. Protocol Violations and Deviations

Protocol violations are defined as departures from accepted clinical research practices or SOAP1 Study protocol or procedures that pose a risk to participant safety, adversely affect data quality and the integrity of the major scientific goals of the study, and/or involve a significant and repeated breach of participants’ privacy. Protocol violations include, but are not limited to:

- failure to obtain or document informed consent prior to study procedures
- randomization of an ineligible participant
- assignment of incorrect CPAP unit
- failure to report serious adverse events appropriately
- breach of confidentiality
- unmasking of participant or staff

By the nature of their definition, protocol violations are considered the most serious class of departure from the study protocol.

## Sleep-Disordered Breathing, Obesity and Pregnancy, Protocol 1 (SOAP1)

---

All protocol violations must be reported on a Protocol Deviation/Violation Form (PD). In addition, within seven days, the site PI must develop an action plan, indicating how the problem has been/will be corrected and reoccurrences prevented. This action plan must be sent to the University of Pittsburgh HRPO and forwarded, along with responses from the HRPO, to the DCC.

Protocol deviations are defined as departures from SOAP1 Study protocol or procedures that do not pose a risk to subject safety, do not adversely affect the integrity of the major scientific goals of the study, and do not involve a significant and repeated breach of participant privacy. Protocol deviations include, but are not limited to:

- failure to obtain appropriate source documentation
- mistimed procedures or visit (e.g., conducting a clinic visit outside of the window outlined in the protocol)
- failure to collect a specimen or perform a test specified in the Protocol
- administrative error

All protocol deviations must be reported on a Protocol Deviation/Violation Form (PD). If a pattern of repeated protocol deviations emerges and it appears that data quality could be compromised or participant safety jeopardized, the PI is expected to investigate to determine whether a protocol violation applies.

